- Immunosuppressive medications have been removed from the prohibited therapy section (Section 4.4.2) and added to the permitted therapy section (Section 4.4.1) to align with atezolizumab management guidelines in Appendix 9 that permit use of immunosuppressive medications for the treatment of corticosteroid-refractory immune-mediated adverse events.
- List of identified risks for atezolizumab have been revised to include severe cutaneous adverse reactions (Section 5.1.1).
- Text has been added to clarify that hemophagocytic lymphohistiocytosis (HLH) and macrophage activation syndrome (MAS) are considered potential risks for atezolizumab (Section 5.1.1, Appendix 9).
- To address a request by the French National Agency for the Safety of Medicines and Health Products (ANSM), HLH and MAS have replaced systemic inflammatory response syndrome on the list of atezolizumab-associated adverse events of special interest (Section 5.2.3).
- Influenza-like illness was removed from the list of immediately reportable adverse events of special interest as enough information regarding such events has been collected, in general is infrequently reported, and is a known adverse event of atezolizumab (Section 5.2.3).
- Text has been added to clarify that adverse events associated with special situations that also qualify as adverse events of special interest should be reported within 24 hours (Section 5.3.5.12).
- Text has been added to indicate that the Informed Consent Form will instruct female patients to inform the investigator if they become pregnant (Section 5.4.3.1).
- The name of a Roche policy on data sharing has been corrected (Section 9.5).
- Appendix 5 was revised to indicate that caution should be used when considering atezolizumab for patients who have previously experienced a severe or life-threatening skin adverse reaction while receiving another immunostimulatory anti-cancer agent.
- To address a request by the French ANSM, the management guidelines for infusion-related reactions associated with atezolizumab have been updated to

include guidelines for cytokine-release syndrome (CRS) to align with the definition, grading, and management of CRS reflected in a recent publication (Lee et al. 2019) (Appendix 9).

- Guidelines for management of atezolizumab-associated dermatological adverse events have been revised to provide guidance on severe cutaneous adverse reactions of Stevens-Johnson syndrome and toxic epidermal necrolysis (Appendix 9).
- The management guidelines for Grade 4 myositis have been removed because Version 4.0 of the Common Terminology Criteria for Adverse Events does not have a Grade 4 category for myositis (Appendix 9).
- To address a request by the French ANSM, the management guidelines for HLH and MAS have been modified to indicate that HLH should be considered when CRS presentation is atypical or prolonged, to add anticytokine therapy as an option for treating HLH or MAS, and to suggest that published guidelines should be followed for HLH or MAS events that do not respond to treatment within 24 hours (Appendix 9).

Additional clarifications have been included, and minor changes have been made to improve clarity and consistency. Substantive new information appears in *italics*. This amendment represents cumulative changes to the original protocol.

PROTOCOL AMENDMENT, VERSION 6.0: SUMMARY OF CHANGES

Section 1.2: Background on Atezolizumab

[...]

Atezolizumab is approved for the treatment of urothelial carcinoma, non–small cell lung cancer, small-cell lung cancer, triple-negative breast cancer, hepatocellular carcinoma, and melanoma.

Section 1.3: Study Rationale and Benefit-Risk Assessment

[...]

This study will enroll patients with NSCLC. Given the relatively poor prognosis and limited treatment options for these patients, this population is considered appropriate for trials of novel therapeutic candidates. The benefit–risk ratio for atezolizumab is expected to be acceptable in this setting.

In the setting of the COVID-19 pandemic, patients with comorbidities, including those with cancer, are considered a more vulnerable population, with the potential for more severe clinical outcomes from COVID-19. However, it is unclear whether or how systemic cancer therapies such as chemotherapy, targeted therapy, or immunotherapy impact the incidence or severity of COVID-19.

A possible consequence of inhibiting the PD-1/PD-L1 pathway may be the modulation of the host immune response to acute infection, which may result in immunopathology or dysregulated immune system defenses. In nonclinical models, PD-1/PD-L1 blockade appears to be associated with serious exacerbation of inflammation in the setting of acute (as opposed to chronic) viral infection with lymphocytic choriomeningitis virus (Clone 13) (85). However, there are insufficient and inconsistent clinical data to assess if outcome from COVID-19 is altered by cancer immunotherapy.

Severe COVID-19 appears to be associated with a cytokine-release syndrome (CRS) involving the inflammatory cytokines interleukin (IL)-6, IL-10, IL-2, and interferon- γ (86). While it is not known, there may be a potential for an increased risk of an enhanced inflammatory response if a patient develops acute SARS-CoV-2 infection while receiving atezolizumab. At this time, there is insufficient evidence for causal association between atezolizumab and an increased risk of severe outcomes from COVID-19.

There may be potential synergy or overlap in clinical and radiologic features for immune-mediated pulmonary toxicity with atezolizumab and clinical and radiologic features for COVID-19–related interstitial pneumonia. Thus, investigators should use their clinical judgment when evaluating and managing patients with pulmonary symptoms.

Section 4.3.3: Investigational Medicinal Product Accountability

[...] The study site is responsible for maintaining records of IMP delivery to the site, IMP inventory at the site, IMP use by each patient, and disposition or return of unused IMP, thus enabling reconciliation of all IMP received, and for ensuring that patients are provided with doses specified by the protocol.

The study site should follow all instructions included with each shipment of IMP. [...] The investigator or designee must confirm that appropriate temperature conditions have been maintained during transit, either by time monitoring (shipment arrival date and time) or temperature monitoring, for all IMPs received and that any discrepancies have been reported and resolved before use of the IMPs. All IMPs must be stored in a secure, environmentally controlled, and monitored (manual or automated) area in accordance with the labeled storage conditions, with access limited to the investigator and authorized staff.

Only patients enrolled in the study may receive IMPs, and only authorized staff may supply or administer IMPs.

[...]

Refer to the pharmacy manual and/or the atezolizumab Investigator's Brochure for information on IMP handling, including preparation and storage, and accountability.

Section 4.4.1: Permitted Therapy

[...]

- Systemic corticosteroids, *immunosuppressive medications*, and tumor necrosis factor- α inhibitors may attenuate potential beneficial immunologic effects of treatment with atezolizumab, but may be administered at the discretion of the treating physician after consultation with the Medical Monitor (see Exclusion Criterion 21 [Section 4.1.2] and Prohibited Therapy [Section 4.4.2]). [...]

Section 4.4.2: Prohibited Therapy

[...]

~~With the exception of autoimmune disease patients, patients should not receive immunosuppressive medications, including but not limited to cyclophosphamide, azathioprine, methotrexate, and thalidomide. These agents could potentially alter the activity and the safety of atezolizumab.~~

Systemic corticosteroids, *immunosuppressive medications*, and anti-TNF- α agents may attenuate potential beneficial immunologic effects of treatment with atezolizumab, but

may be administered at the discretion of the treating physician after consultation with the Medical Monitor.

Section 5.1: Safety Plan

[...]

Patients with active infection are excluded from study participation. In the setting of a pandemic or epidemic, screening for active infections (including SARS-CoV-2) prior to and during study participation should be considered according to local or institutional guidelines or guidelines of applicable professional societies (e.g., American Society of Clinical Oncology or European Society for Medical Oncology).

Severe COVID-19 appears to be associated with a CRS involving the inflammatory cytokines IL-6, IL-10, IL-2, and IFN- γ (86). If a patient develops suspected CRS during the study, a differential diagnosis should include COVID-19, which should be confirmed or refuted through assessment of exposure history, appropriate laboratory testing, and clinical or radiologic evaluations per investigator judgment. If a diagnosis of COVID-19 is confirmed, the disease should be managed as per local or institutional guidelines.

Section 5.1.1: Risks Associated with Atezolizumab

Atezolizumab has been associated with risks such as the following: IRRs and immune-related hepatitis, pneumonitis, colitis, pancreatitis, diabetes mellitus, hypothyroidism, hyperthyroidism, adrenal insufficiency, hypophysitis, Guillain-Barré syndrome, myasthenic syndrome or myasthenia gravis, meningoencephalitis, myocarditis, nephritis, and myositis, and severe cutaneous adverse reactions.

Immune-related reactions may involve any organ system and may lead to hemophagocytic lymphohistiocytosis (HLH) and macrophage activation syndrome (MAS), which are considered to be potential risks for atezolizumab. [...]

Section 5.2.3: Adverse Events of Special Interest (Immediately Reportable to the Sponsor)

[...]

- Events suggestive of hypersensitivity, infusion-related reactions, cytokine-release syndrome, HLH, and MAS ~~influenza-like illness, and systemic inflammatory response syndrome~~

[...]

Section 5.3.5.12: Cases of Overdose or Medication Error

[...] If the associated adverse event fulfills seriousness criteria or qualifies as an adverse event of special interest, the event should be reported to the Sponsor immediately (i.e., no more than 24 hours after learning of the event; see Section 5.4.2). [...]

Section 5.4.3.1: Pregnancies in Female Patients

Female patients of childbearing potential will be instructed *through the Informed Consent Form* to immediately inform the investigator if they become pregnant during the study or within 5 months after the last dose of atezolizumab or within 6 months after the last dose of single agent chemotherapy. [...]

Section 9.5: Dissemination of Data and Protection of Trade Secrets

[...] For more information, refer to the Roche Global Policy on Sharing of Clinical Trials Data *Study Information* at the following website:

[...]

Section 10: References

[...]

[...]

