Immune-mediated myositis, Grade 4	
Permanently discontinue atezolizumab and contact Medical Monitor.^cRefer patient to rheumatologist or neurologist.Initiate treatment as per institutional guidelines.Respiratory support may be required in more severe cases.Initiate treatment with corticosteroids equivalent to 1-2 mg/kg/day IV methylprednisolone, or higher-dose bolus if patient is severely compromised (e.g., cardiac or respiratory symptoms, dysphagia, or weakness that severely limits mobility); convert to 1-2 mg/kg/day oral prednisone or equivalent upon improvement.If event does not improve within 48 hours after initiating corticosteroids, consider adding an immunosuppressive agent.If event resolves to Grade 1 or better, taper corticosteroids over ≥ 1 month.

[...]

HEMOPHAGOCYTIC LYMPHOHISTIOCYTOSIS AND MACROPHAGE ACTIVATION SYNDROME

Immune-mediated reactions may involve any organ system and may lead to HLH and MAS, which are considered to be potential risks for atezolizumab.

Clinical and laboratory features of severe CRS overlap with HLH, and HLH should be considered when CRS presentation is atypical or prolonged.

[...]

Table 14 Management Guidelines for Suspected Hemophagocytic Lymphohistiocytosis or Macrophage Activation Syndrome

Event	Management
Suspected HLH or MAS	
• Permanently discontinue atezolizumab and contact Medical Monitor.• Consider patient referral to hematologist.• Initiate supportive care, including intensive care monitoring if indicated per institutional guidelines.• Consider initiation of IV corticosteroids, and/or an immunosuppressive agent, and/or anti-cytokine therapy.• If event does not respond to treatment within 24 hours, contact Medical Monitor and initiate treatment as appropriate according to published guidelines (La Rosée 2015; Schram and Berliner 2015; La Rosée et al. 2019)if event does not improve within 48 hours after initiating corticosteroids, consider adding an immunosuppressive agent.• If event resolves to Grade 1 or better, taper corticosteroids over \geq 1 month.

HLH = hemophagocytic lymphohistiocytosis; MAS = macrophage activation syndrome.

REFERENCES

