5.1.2 Management of Patients Who Experience Specific Adverse Events

There will be no dose modifications for atezolizumab in this study.

Atezolizumab may be temporarily suspended in patients who experience toxicity considered to be related to study treatment. If atezolizumab is withheld for > 12 weeks after event onset, the patient will be discontinued from study drug. If the investigator believes the patient is likely to derive clinical benefit and the Medical Monitor is in agreement, atezolizumab can be resumed after being withheld for > 12 weeks after event onset.

If a patient must be tapered off steroids that have been used to treat adverse events, then atezolizumab may be withheld for more than 12 weeks after event onset until the steroids are discontinued or reduced to a prednisone dose (or dose equivalent) of \leq 10 mg/day. For patients with CNS metastases or autoimmune disease who require chronic steroid therapy, who have been receiving additional steroids to treat adverse events, and who now require a reduction in steroid dosage, atezolizumab may be withheld for more than 12 weeks after event onset until the steroid dosage has returned

to its baseline value. The investigator and the Medical Monitor will determine the acceptable length of treatment interruption.

Dose interruptions for reasons other than toxicity (e.g., surgical procedures) may be allowed with Medical Monitor approval. The investigator and the Medical Monitor will determine the acceptable length of treatment interruption.

Given the mechanism of action of atezolizumab, events associated with inflammation and/or immune-related adverse events (irAEs) have been closely monitored during the atezolizumab clinical program. Guidelines for the management of patients who experience specific adverse events associated with atezolizumab (i.e., pulmonary, hepatic, gastrointestinal, endocrine, ocular, infusion-related [IRR], pancreatic, dermatologic, neurologic, or autoimmune events) are provided in [Appendix 9](#) and Section 6 (Guidance for the Investigator) of the Atezolizumab Investigator's Brochure.

For patients developing a new autoimmune disease not listed in the Atezolizumab Investigator's Brochure, or for patients with an autoimmune disease who develop a flare, the following dosing guidance should be applied:

- Grade 1 event: atezolizumab dosage should be maintained

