Dermatologic event, Grade 3	
 Withhold atezolizumab for up to 12 weeks after event onset.^a Refer patient to dermatologist for evaluation and, if indicated, biopsy. Initiate treatment with corticosteroids equivalent to 10 mg/day oral prednisone, increasing dose to 1–2 mg/kg/day if event does not improve within 48–72 hours. If event resolves to Grade 1 or better, resume atezolizumab.^b If event does not resolve to Grade 1 or better while withholding atezolizumab, permanently discontinue atezolizumab and contact Medical Monitor.^c
Dermatologic event, Grade 4	
 Permanently discontinue atezolizumab and contact Medical Monitor.^c
Stevens-Johnson syndrome or toxic epidermal necrolysis (any grade)	
Additional guidance for Stevens-Johnson syndrome or toxic epidermal necrolysis:
 
 Withhold atezolizumab for suspected Stevens-Johnson syndrome or toxic epidermal necrolysis. Confirm diagnosis by referring patient to a specialist (dermatologist, ophthalmologist or urologist as relevant) for evaluation and, if indicated, biopsy. Follow the applicable treatment and management guidelines above. If Stevens-Johnson syndrome or toxic epidermal necrolysis, permanently discontinue atezolizumab.

^a Atezolizumab may be withheld for a longer period of time (i.e., >12 weeks after event onset) to allow for corticosteroids (if initiated) to be reduced to the equivalent of ≤10 mg/day oral prednisone. The acceptable length of the extended period of time must be agreed upon by the investigator and the Medical Monitor.

^b If corticosteroids have been initiated, they must be tapered over ≥1 month to the equivalent of ≤10 mg/day oral prednisone before atezolizumab can be resumed.

^c Resumption of atezolizumab may be considered in patients who are deriving benefit and have fully recovered from the event. Patients can be re-challenged with atezolizumab only after approval has been documented by both the investigator (or an appropriate delegate) and the Medical Monitor.

NEUROLOGIC DISORDERS

Myasthenia gravis and Guillain-Barré syndrome have been observed with single-agent atezolizumab. Patients may present with signs and symptoms of sensory and/or motor neuropathy. Diagnostic workup is essential for an accurate characterization to differentiate between alternative etiologies. Management guidelines for neurologic disorders are provided in [Table 10](#).

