Immune-related myositis has been associated with the administration of atezolizumab. Myositis or inflammatory myopathies are a group of disorders sharing the common feature of inflammatory muscle injury; dermatomyositis and polymyositis are among the most common disorders. Initial diagnosis is based on clinical (muscle weakness, muscle pain, skin rash in dermatomyositis), biochemical (serum creatine kinase increase), and imaging (electromyography/MRI) features, and is confirmed with a muscle biopsy.

Patients with signs and symptoms of myositis, in the absence of an identified alternate etiology, should be treated according to the guidelines in [Table 13](#).

Table 13 Management Guidelines for Immune-Related Myositis

Event	Management
Immune-related myositis, Grade 1	
Continue atezolizumab.Refer patient to rheumatologist or neurologist.Initiate treatment as per institutional guidelines.
Immune-related myositis, Grade 2	
Withhold atezolizumab for up to 12 weeks after event onset^a and contact Medical Monitor.Refer patient to rheumatologist or neurologist.Initiate treatment as per institutional guidelines.Consider treatment with corticosteroids equivalent to 1–2 mg/kg/day IV methylprednisolone and convert to 1–2 mg/kg/day oral prednisone or equivalent upon improvement.If corticosteroids are initiated and event does not improve within 48 hours after initiating corticosteroids, consider adding an immunosuppressive agent.If event resolves to Grade 1 or better, resume atezolizumab.^bIf event does not resolve to Grade 1 or better while withholding atezolizumab, permanently discontinue atezolizumab and contact Medical Monitor.^c

^a Atezolizumab may be withheld for a longer period of time (i.e., > 12 weeks after event onset) to allow for corticosteroids (if initiated) to be reduced to the equivalent of ≤ 10 mg/day oral prednisone. The acceptable length of the extended period of time must be agreed upon by the investigator and the Medical Monitor.

^b If corticosteroids have been initiated, they must be tapered over ≥ 1 month to the equivalent of ≤ 10 mg/day oral prednisone before atezolizumab can be resumed.

^c Resumption of atezolizumab may be considered in patients who are deriving benefit and have fully recovered from the event. Patients can be re-challenged with atezolizumab only after approval has been documented by both the investigator (or an appropriate delegate) and the Medical Monitor.

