Table 13 Management Guidelines for Immune-Related Myositis (cont.)

Immune-related myositis, Grade 3	
Withhold atezolizumab for up to 12 weeks after event onset^a and contact Medical Monitor.Refer patient to rheumatologist or neurologist.Initiate treatment as per institutional guidelines.Respiratory support may be required in more severe cases.Initiate treatment with corticosteroids equivalent to 1-2 mg/kg/day IV methylprednisolone, or higher-dose bolus if patient is severely compromised (e.g., cardiac or respiratory symptoms, dysphagia, or weakness that severely limits mobility); convert to 1-2 mg/kg/day oral prednisone or equivalent upon improvement.If event does not improve within 48 hours after initiating corticosteroids, consider adding an immunosuppressive agent.If event resolves to Grade 1 or better, resume atezolizumab.^bIf event does not resolve to Grade 1 or better while withholding atezolizumab, permanently discontinue atezolizumab and contact Medical Monitor.^cFor recurrent events, treat as a Grade 4 event.
----------------------------------	--

^a Atezolizumab may be withheld for a longer period of time (i.e., > 12 weeks after event onset) to allow for corticosteroids (if initiated) to be reduced to the equivalent of ≤ 10 mg/day oral prednisone. The acceptable length of the extended period of time must be agreed upon by the investigator and the Medical Monitor.

^b If corticosteroids have been initiated, they must be tapered over ≥ 1 month to the equivalent of ≤ 10 mg/day oral prednisone before atezolizumab can be resumed.

^c Resumption of atezolizumab may be considered in patients who are deriving benefit and have fully recovered from the event. Patients can be re-challenged with atezolizumab only after approval has been documented by both the investigator (or an appropriate delegate) and the Medical Monitor.

HEMOPHAGOCYTIC LYMPHOHISTIOCYTOSIS AND MACROPHAGE ACTIVATION SYNDROME

Immune-related reactions may involve any organ system and may lead to hemophagocytic lymphohistiocytosis (HLH) and macrophage activation syndrome (MAS), which are considered to be potential risks for atezolizumab.

Clinical and laboratory features of severe CRS overlap with HLH, and HLH should be considered when CRS presentation is atypical or prolonged.

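### Recurrent Grade 3 immune-related myositis is sent to a Grade 4 row that Version 6 deleted, so stop or resume is undefined

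*Protocol*

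**What the plan says.** The Version 6 rationale at the front of the protocol states: "The management guidelines for Grade 4 myositis have been removed because Version 4.0 of the Common Terminology Criteria for Adverse Events" does not include that grade for myositis.

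Current Appendix 9, Table 13 has rows for Grades 1, 2 and 3, followed directly by its footnotes. The Grade 3 row opens with "Withhold atezolizumab for up to 12 weeks after event onset" together with Medical Monitor contact. It goes on to referral, respiratory support and intravenous corticosteroids, then "If event does not improve within 48 hours after initiating corticosteroids, consider adding an immunosuppressive agent". On dosing it says "If event resolves to Grade 1 or better, resume atezolizumab", and for the other outcome "If event does not resolve to Grade 1 or better while withholding atezolizumab, permanently discontinue atezolizumab and contact Medical Monitor". Its last line tells sites to treat a recurrence as though it were Grade 4.

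The removed row, headed "Immune-mediated myositis, Grade 4", can be seen only in the Version 6 Summary of Changes. Its first instruction was permanent discontinuation.

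**The concern.** A safety dosing instruction in the current protocol refers to a grade for which the same table has no guidance, and which the protocol says its grading scale lacks for this event. A site facing a recurrent Grade 3 case cannot follow that line as written. The instruction it can follow, a few lines higher in the same cell, is to resume once the event has settled.

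Myositis is a listed atezolizumab risk (Section 5.1.1) and an adverse event of special interest (Section 5.2.3). The Grade 3 row itself contemplates cardiac or respiratory symptoms and dysphagia. At stake is whether a patient whose severe myositis has come back is re-exposed under the ordinary resume line or stopped, and whether sites answer that question in the same way.

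**Working it through.** No plan figure needs reproducing, so the check is mainly a comparison of texts.

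**1. Is the row really absent?** Yes. The rationale confirms a deliberate removal, so this is not a loss in PDF conversion. Nor is it just a difference between the amendment log and the current text: the pointer and the missing target are both in current Table 13. The log only explains how the gap arose.

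**2. Which rows use the pointer?** Only Grade 3. The Grade 1 row continues drug with referral. The Grade 2 row has its own withhold, resume and stop rules, including "If corticosteroids are initiated and event does not improve within 48 hours after initiating corticosteroids, consider adding an immunosuppressive agent", and does not refer to Grade 4.

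**3. What did the deletion remove?**

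| Step | Current Grade 3 row | Deleted Grade 4 row |
|---|---|---|
| Dosing at onset | Withhold up to 12 weeks; Medical Monitor | Stop permanently; Medical Monitor |
| Referral, institutional treatment, respiratory support | Yes | Same |
| Corticosteroid dose; 48-hour immunosuppressant step | Yes | Same |
| Steroid taper of at least 1 month | Footnote b, before resuming | In the row |
| After resolution to Grade 1 | Resume, subject to footnote b | Re-challenge only under footnote c |
| No resolution | Stop permanently | Already stopped |

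The loss is one rule: automatic permanent discontinuation at recurrence. With it goes footnote c's condition that re-challenge needs documented approval from both the investigator and the Medical Monitor. The Grade 3 resume line carries no such condition.

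**4. How do other Appendix 9 tables handle recurrence?** Table 1 sends recurrent Grade 2 pulmonary events to a Grade 3 or 4 row that exists. Table 4 sends recurrent hypophysitis to a Grade 4 row that exists. Table 8 uses no pointer: it states outright that recurrent pancreatic events mean permanent discontinuation and Medical Monitor contact. Among these, only the myositis instruction lacks a target.

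**5. Do the general rules fill the gap?**
- Section 5.1.2: "If atezolizumab is withheld for > 12 weeks after event onset, the patient will be discontinued from study drug". This depends on how long drug is withheld, not on recurrence, and has exceptions.
- Section 4.6.2 requires stopping for intolerable related toxicity. That is a judgement, not a recurrence rule.
- Section 5.1.2 also stops drug for Grade 4 autoimmune events, but only for a new autoimmune disease not in the Investigator's Brochure or a flare of existing disease. Section 5.1.1 already lists myositis as a risk of the drug.

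**6. How many patients?** Incidence is an assumption: 600 × 0.002 = 1.2 and 600 × 0.01 = 6, so about 1 to 6 patients with any myositis. Recurrent Grade 3 cases would be fewer, possibly none.

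**7. Does it reach the primary analysis?** The immune-related endpoint is an incidence with Clopper-Pearson limits (SAP Section 3.5.2), and the adverse event tables count patients with at least one event (SAP Section 3.5.3). A first Grade 3 episode judged related, and treated with systemic corticosteroids as the row directs, already makes the patient a case. A recurrence adds no new patient.

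**The case against.** The best case against is that this is a stale cross-reference with an obvious meaning. Treating an event as Grade 4 can only mean something stricter than the Grade 3 row, and the Grade 4 rows for colitis, hypophysitis, pancreatitis and dermatologic events all require permanent discontinuation. The Grade 3 row also brings in the Medical Monitor at the outset, so no site decides alone. The deleted row was not absolute either, since footnote c allowed re-challenge. Section 5.1.2 also sends investigators to Section 6 of the Investigator's Brochure, which is not available here and may say more.

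Much of this stands, and it limits the point. It does not remove it. The inference from other organ systems is reasonable but is not a stated rule, and not every Grade 4 row stops drug: Table 4 has Grade 4 hyperglycemia withheld and resumed. Contacting the Medical Monitor is not the documented two-party approval that footnote c requires. What the Brochure says cannot be settled from these documents, and it would not repair a line in the protocol that cannot be followed.

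A reader might infer more: that recurrent myositis is left with no management or stopping instruction, or that Grade 3 now offers only withholding and resuming. The row comparison contradicts both.

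**Conclusion.** The Grade 3 recurrence line is wrong as written and should be corrected on patient-safety grounds. What is undefined is one decision: at a recurrence of Grade 3 myositis, stop permanently or go through another withhold-and-resume cycle.

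The number affected is small, and the range given rests on an assumed incidence. A reader might also infer that the immune-related co-primary endpoint is distorted. The documents do not support that, because incidence counts patients and a patient with a recurrence will ordinarily have been counted at the first episode. The sample size and analysis methods are untouched.

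**What to change.** In Appendix 9, Table 13, replace the last line of the Grade 3 cell with the rule Table 8 already uses for recurrent pancreatitis: for recurrent events, discontinue atezolizumab permanently and contact the Medical Monitor, with footnote c attached. This restores the action of the deleted row without reviving a grade that the scale lacks. The sponsor's clinicians should confirm that this is the intended rule. If they intend another withhold-and-resume cycle instead, the cell should say so.

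Send a short clarification to sites. The cost is one table cell and one letter, with no change to data collection or analysis.
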